### **Process Evaluation Indicators**

1.	Module 1 : Knowing your mental health	modul_1_a- modul_1_e	Assessment the comprehension of the modul 1 content.	0= False 1=True
2.	Modul 2A	hw_image_aktiviti1 Apakah aktiviti yang akan anda buat untuk memperbaiki isu ? Aktiviti 1: Contoh : mula mencari bantuan kewangan, cari maklumat atas talian, tanya ketua komuniti	Identified the major issues and suggest solution to overcome based on the resilient strength	Open ended
		resilien_aktiviti1		
		kekuatan minda untuk capai		
		Aktiviti 1 Contoh kuat imam, minta kekuatan		
		dari tuhan		
		hw_image_v3 Apakah Elemen (Isu-isu) yang perlu dibaiki? Elemen /isu no 2: isu kesihatan, kurangkan rokok , kurang senam		
		hw_image_aktiviti2 Apakah aktiviti yang akan anda buat untuk memperbaiki isu ?		
		Aktiviti 2: Contoh bersenam selalu/ berhenti		
		rokok		
		resilien_aktiviti2 kekuatan minda untuk capai		
		Aktiviti 2		

		Contoh sebelum ini anda orang yang berdisiplin		
3	Modul 2B	modulquiz_2b_a- modulquiz_2b_b https://docs.google.com/forms/d/e/1F AIpQLScneTULuCPu4aYHajYu6Zc PbNnflrO3L0hHxpGbiviGNarAHg/v iewform?usp=sf_link APPENDIX	

Behaviour Activation

Weekly monitoring form for activities

	0= False 1=True
4	Modul 2C	modul_2c_a- modul_2c_b https://docs.google.com/forms/d/e/1F AIpQLSe2EwdTv6497vwex695cbm N77QdRRZDT8VymOL4GhrQFifu1 Q/viewform?usp=sf_link APPENDIX	- Understanding negative thought and overcome it	0= False 1=True
5	Modul 2D	modulquiz_2d_a- modulquiz_2d_e Mindful Attention Awareness Scale (MAAS) maas_1a- maas_15a	To assess the understanding of mindful breathing and practice of the mindfulness breathing	1= almost always 2= frequently 3=very frequently 4=some what infrequent 5=very infrequent 6= almost never
6.	Modul 3	modulquiz_3_a- modulquiz_3_e	To be aware of the reliable source to seek help	0= False 1=True

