	Pernafasan (Mindfulness)	Quiz dan Soal selidik Minfulness Awareness	35 minit	
Modul 3 · Me	endapatkan Bantuan	Quiz	15 minit	
		Video	15 minit	
	Total			

[figure not shown]

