#### 3.2.3.2 Control Group

Respondents selected in the control arm will be given a copy of Healthy Mind Modules, Let's TALK pamphlets and an educational video from the Malaysia Ministry of Health (MOH, 2005, 2018). And they will be given the intervention arm module or material at the end of the study **Figure 3.3** 

3.2.3.1a Proses Evaluation

To determine whether programme activities have been implemented as intended. An analytical comparison of planned processes versus actual implementation, determination of strengths and weaknesses of the programme were conducted. Each participant will be monitored with a log from the REDCap online database on the completion of the training sessions and pre-test and post-test scoring of the modules quizzes. The percentage of the execution of tasks, attendance of the training sessions and pre-test and post-test/quizzes scoring of the online modules will be taken as an indicator of the quality and fidelity of the Reshape intervention modules.

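### The codebook key for the 15-item mindfulness scale in Module 2D transposes codes 2 and 3, so 'very frequently' scores as less frequent than 'frequently'

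*Protocol*

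**What the plan says.** Table 3.7 (section 3.2.7.1) ends with a block of process evaluation indicators. Its Modul 2D row lists two instruments: a five-item quiz (modulquiz_2d_a to modulquiz_2d_e) and the "Mindful Attention Awareness Scale (MAAS) maas_1a- maas_15a". The stated purpose of the row is "To assess the understanding of mindful breathing and practice of the mindfulness breathing". The measurement column gives the key "1= almost always 2= frequently 3=very frequently 4=some what infrequent 5=very infrequent 6= almost never".

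Table 3.1 (section 3.1.3) shows the scale as part of the Module 2D assignment: "Quiz dan Soal selidik Minfulness Awareness". The process evaluation text that follows the Control Group paragraph in section 3.2.3.2 says that task execution, attendance and quiz scoring "will be taken as an indicator of the quality and fidelity of the Reshape intervention modules". The logic model (Figure 3.2, section 3.2.3) also counts the total scoring of the assignments among its outputs.

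The key appears nowhere else in the Protocol. No other section corrects it, and none says how the 15 items are to be combined.

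**The concern.** The key starts at 'almost always' and ends at 'almost never', so a higher code should mean that something happens less often. The lower end follows this rule: somewhat infrequent (4), very infrequent (5), almost never (6). The upper end does not. 'Very frequently' must lie between 'almost always' and 'frequently', yet it comes after 'frequently'. This can be seen from the labels alone, without the scale's manual.

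Mindful breathing is one of the named active components of the ReSHape modules, and this scale is one of the two indicators listed for it. If the written key carries through to the REDCap form or to the analysis labels, two of the six answers change places. A respondent who moves from 'very frequently' to 'frequently' is moving towards 'almost never', but the item score falls from 3 to 2 when it should rise from 2 to 3. Any description of Module 2D that uses these item scores would carry that error.

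**Working it through.** **Inputs, all from the Modul 2D row of Table 3.7:** six labels with their codes, and 15 items (maas_1a to maas_15a). The Protocol gives no total, mean or cut-off for this scale, so there is no planned figure to reproduce.

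**Step 1. Compare each code with the frequency rank of its label (1 = most often).**

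| Label | Code as written | Frequency rank | Error (code − rank) |
|---|---|---|---|
| almost always | 1 | 1 | 0 |
| frequently | 2 | 3 | −1 |
| very frequently | 3 | 2 | +1 |
| somewhat infrequent | 4 | 4 | 0 |
| very infrequent | 5 | 5 | 0 |
| almost never | 6 | 6 | 0 |

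Six labels form 6 × 5 / 2 = 15 pairs. Exactly one pair is inverted ('frequently' and 'very frequently'); the other 14 are in order. 'Almost always' stays below both, and codes 1 to 3 all stay below codes 4 to 6.

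**Step 2. Error for one respondent.** Let V be the number of 'very frequently' answers and F the number of 'frequently' answers, with V + F at most 15. If the items are summed (assumption):

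error in total = (+1) × V + (−1) × F = V − F.

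The possible total runs from 15 × 1 = 15 to 15 × 6 = 90, a span of 75 points.

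- All 15 'very frequently': recorded 15 × 3 = 45, should be 15 × 2 = 30, error +15.
- All 15 'frequently': recorded 15 × 2 = 30, should be 15 × 3 = 45, error −15.
- Mixed, for example V = 8 and F = 7: error 8 − 7 = +1.
- No answers in either category: error 0.

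The absolute error is therefore between 0 and 15 points, at most 15 / 75 = 20% of the span. If the items are averaged instead, the limit is 15 / 15 = 1 point.

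The two uniform records show the reversal most clearly. The true difference, 'frequently' minus 'very frequently', is 45 − 30 = +15; the written key gives 30 − 45 = −15. These are bounds, not expected values. The typical error depends on how answers are distributed, which the Protocol does not tell us.

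**Step 3. Check after correction.** With 'very frequently' at 2 and 'frequently' at 3, every error in the table is 0 and no pair is inverted.

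**Step 4. Could text extraction have caused this?** It is unlikely. All six labels stand in one cell, in numerical order, each next to its number. Broken table extraction moves cells; it does not usually exchange words between neighbouring numbers in a running string.

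**The case against.** The strongest reply is that no mis-scored answer has been shown. The modules are delivered in Malay (section 3.1.3), and the English labels in Table 3.7 may only gloss a Malay form that is not in the document. If that form is correctly ordered, the fault is a slip in the codebook and no data are wrong. This stands, and it is why the remedy begins with a check of the form.

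The second reply is that the Protocol does not clearly use a score from this scale. Sections 3.2.3.1 and 3.2.3.2 rest fidelity on task completion, attendance, quiz scores and submission of assignments, and a submitted form counts the same under either key. This largely stands. The logic model does list the total scoring of the assignments as an output, but it does not name this scale.

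A reader might infer more than the document supports in three ways:

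- That a measured change in mindfulness would be biased. No such change is planned. The scale is listed only within Module 2D and is not among the instruments given for baseline and post-test in the Outcome Evaluation section.
- That Module 2D would be left without a sound indicator. The five-item quiz stands in the same row and is unaffected.
- That the whole frequent end of the scale is disordered. Only one adjacent pair is inverted.

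**Conclusion.** The key is wrong as written, and the document alone shows it. This is a minor coding error in one codebook cell. Its effect per item is +1 for 'very frequently', −1 for 'frequently' and nothing for the other four codes. The bound of 15 points on a 15 to 90 range assumes that the items are summed and that all 15 answers fall in one of the two affected categories; mixed answers partly cancel.

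Whether any data are affected depends on the label order of the fielded form, which the document does not show. The reach is limited to the Module 2D process evaluation. PHQ-9, GAD-7, EQ-5D-5L, the secondary outcomes, the comparison between arms and the sample size do not depend on this key.

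**What to change.** 1. In Table 3.7, correct the key to 1 = almost always, 2 = very frequently, 3 = frequently, 4 = somewhat infrequently, 5 = very infrequently, 6 = almost never.
2. Check the order of the labels and their stored codes on the Malay REDCap form.
3. Swap codes 2 and 3 in the data only if that check shows that answers were captured under the written key. Recoding correctly captured data would create the very error that the swap is meant to remove.

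The cost is one codebook line, one look at the form and, if needed, one recode statement. No new data are required.

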#### 3.2.7.2 Data analysis

The preliminary raw data will be retrieved from REDCap and was organised before it is imported to STATA version 17.0 for statistical analysis. All the data interpretation will be based on the significant level of 0.05 with a power of 80%.

#### a. Descriptive Analyses

Preliminary descriptive data analyses involved exploration of the dataset to understand the data structure, distribution of the values, identification of extreme values, and missingness within the dataset. Subsequently, descriptive statistics will be used to compare the intervention and control groups' baseline characteristics. The results will be presented in counts and proportions for categorical data. Normally distributed data is presented in mean and standard deviation, while skewed data will be summarised with median and interquartile range (IQR).

In order to establish baseline equivalent, respondents characteristics between the treatment and the control group's respondents will be assessed using an independent t-test for normally distributed continuous data, Mann-Whitney U test for skewed data and chi-square test for categorical data.

#### b. Missing Data

The overall missing values will be analyzed using the multiple imputation function in SPSS version 23. The steps in multiple imputations will be followed through, and the missing pattern will be identified as missing at random (MAR). Five imputed datasets will be generated for the monotone missing pattern. The aggregation function in SPSS version 23 will be used to pool the five imputed datasets for univariate analysis and multivariable analysis.

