#### 3.2.5 Sample size calculation

Based on Mathias et al. (2018) study on the effectiveness of resilience intervention to improve the mental status among young women in India and a local study for the effectiveness of mindfulness among university students, the effect size of the pre-test and post-test intervention were (d=0.42)(Phang, Chiang, et al., 2015). The sample size was calculated using G\*Power version 3.1.9.4, and the estimated sample size was 50 cases in each arm (after inflated with a 20 % reserved rate). The initial required sample size for the entire study was calculated based on a 0.05 precision level and a 95 per cent confidence interval with the power of 80 per cent. Experts in module development have suggested that the validation of the modules is similar to the validation for research instruments (Sidek, 2005). Therefore the sample size for validation of modules was 30 respondents, and a similar sample size was observed in other modules' development studies (Ahmad et al.; Talib et al., 2015)

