#### Inferential Analyses

In univariate analysis, paired T-test or Wilcoxon Signed Rank Test will be applied to identify the difference in scores for primary and secondary outcomes of interest for Time-0 and Time-1 in this study. An intergroup mean difference will be calculated based on the formula

mentioned below to confirm the difference between the intervention and the control group's primary and secondary outcomes variables shown in Table 3.15.

Intergroup mean difference = [(mean preI – mean postI) – (mean preC – mean postC)], where preI = pre-intervention in intervention group;

post = post-intervention in intervention group;

prec = pre-intervention in comparison group and

postC = post-intervention in comparison group.

In multivariable analyses, three types of inferential analyses will be considered. They are repeated measures ANOVA, ANCOVA, generalised linear mixed model (GLMM) (Mixed Model Repeated Measure (MMRM) or logistic GLMM). A mixed model general linear model design like repeated measures ANOVA and ANCOVA helped address differences between two independent measures while also exposing subjects to repeated measures (Green & Salkind, 2011; Leppink, 2018). However, they only allowed listwise deletion and last observation carried forward (LOCF) for dropout cases. This may lead to reduced power and biases in the estimation. Therefore, given the missingness for dropout 20%) and small sample size, MMRM or logistic GLMM is superior in conserving the power of the current dataset. MMRM or logistic GLMM is also a likelihood-based statistical approach for handling repeated non-independent measures data collection overtime points. This model uses an unstructured time and covariance structure that (1) avoids model misspecification and (2) its unbiasedness for data that are missing completely at random (MCAR) or missing at random (MAR)(Bell & Rabe, 2020; Mallinckrod+ et al., 2008). GLMM was chosen for analysis instead of GEE, as the formal is an extension of MMRM, providing a more consistent estimate of the fixed effects and given MAR for missingness in the current dataset (Liu and Zhan, 2011; Davis, 2014).

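### Five imputations are too few for tests on data with 20% dropout: a p-value near 0.05 can change sides with the random seed (a minor point, cheap to repair)

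*Protocol*

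**What the plan says.** Under Missing Data (section 3.2.7.2, b) the protocol plans multiple imputation in SPSS: "Five imputed datasets will be generated for the monotone missing pattern". On the mechanism it says that "the missing pattern will be identified as missing at random (MAR"). On use it says: "The aggregation function in SPSS version 23 will be used to pool the five imputed datasets for univariate analysis and multivariable analysis". So the imputed data are meant for both kinds of test.

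Under Inferential Analyses the univariate tests are paired t-tests or Wilcoxon signed rank tests between T0 and T1. The multivariable tests are MMRM or logistic GLMM, preferred over ANOVA and ANCOVA "given the missingness for dropout 20%) and small sample size". The reason given is that these likelihood methods keep the dropouts and are unbiased under MAR.

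The opening of section 3.2.7.2 sets the decision rule: "All the data interpretation will be based on the significant level of 0.05 with a power of 80" per cent. Section 3.2.5 gives the planning values: "the effect size of the pre-test and post-test intervention were (d=0.42"), and "the estimated sample size was 50 cases in each arm (after inflated with a 20 % reserved rate"). Section 3.2.1 schedules only T0 and T1. The protocol gives no reason for five imputations.

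**The concern.** With one post-test visit, a participant who drops out lacks the outcome itself, so about a fifth of the T1 values would be random draws. Averaging over only five draws leaves visible Monte Carlo noise in the pooled estimate and its standard error. Every outcome is judged at a fixed 0.05. Two analysts with the same data and the same plan could therefore report opposite conclusions for a borderline outcome because their seeds differ. With three primary instruments and several secondary ones, a borderline result somewhere is plausible.

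**Working it through.** The protocol reports no Monte Carlo error and no basis for the number five, so there is no figure of its own to reproduce here. The 50 per arm is taken as given; whether it follows from d = 0.42 is a separate question that this point does not depend on.

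**Inputs from the protocol.** Imputations m = 5; dropout 20%, so 50 × 0.8 = 40 completers per arm; effect 0.42 SD; level 0.05.

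**Assumptions.** Two-sided test; equal dropout in both arms; T0–T1 correlation 0.2 to 0.7; Rubin's rules.

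**Step 1, formula.** Let B be the between-imputation variance and T the total variance. The Monte Carlo variance of the pooled estimate is B/m. Since the fraction of missing information is FMI = (1 + 1/m)B/T, the seed-to-seed SD of the test statistic is

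sqrt(FMI / ((1 + 1/m) × m)).

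At FMI 0.2:
- m = 5: sqrt(0.2 / (1.2 × 5)) = 0.18
- m = 50: sqrt(0.2 / (1.02 × 50)) = 0.063

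A result at z = 1.96 then covers these p-values in 95% of re-runs:
- m = 5: z = 1.96 ± 1.96 × 0.183, p from 0.021 to 0.109
- m = 50: z = 1.96 ± 1.96 × 0.063, p from 0.037 to 0.066

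For m = 5 the range is 0.027 to 0.088 at FMI 0.1 and 0.017 to 0.128 at FMI 0.3.

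**Step 2, simulation of borderline results.** The formula leaves out the noise in the estimated variance and degrees of freedom, so it was checked by simulation. T1 was imputed by regression on arm and T0 with parameter draws, and the results were combined by Rubin's rules. In the first two rows, datasets were kept if their p with a large reference number of imputations was 0.03 to 0.08. In the third, they were set to p of about 0.05.

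| Analysis | m | SD over seeds | Seeds on the other side of 0.05 |
|---|---|---|---|
| Difference in change | 5 | 0.19–0.22 | 29–34% |
| Difference in change | 50 | 0.06–0.07 | 10–13% |
| ANCOVA | 5 | 0.25–0.26 | 35–36% |
| ANCOVA | 50 | 0.08 | 15–20% |
| ANCOVA, p about 0.05 | 5 | 0.25–0.26 | 43% below, 57% above |

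In the last row, 90% of re-runs gave p between 0.019 and 0.142; with m = 50 the range was 0.037 to 0.069. The assumed correlation makes little difference.

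**Step 3, all datasets.** The rates in step 2 are conditional on a borderline result. Only 15–17% of datasets fall in the window 0.03 to 0.08 at effect 0.42, and 4–5% under the null. The window alone therefore contributes between 0.15 × 0.29 = 4% and 0.17 × 0.34 = 6% changed decisions. With the datasets outside it, an m = 5 run disagrees with the 400-imputation decision in 6–8% of cases at effect 0.42, and in about 2% or less under the null. With m = 50 the figure at effect 0.42 is about 2%.

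**Step 4, validity.** Under Rubin's rules, null rejection was 4.0–5.0% at m = 5 and 3.9–5.0% at m = 50. Power was 33% against 34% (correlation 0.2) and 45% against 47% (correlation 0.5).

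**Step 5, pooling.** The protocol names SPSS's aggregation function and not Rubin's rules. If that means averaging the five datasets into one, the seed SD remains about 0.2, but the p ranges and changed-decision rates above no longer describe the plan. Null rejection rises to 7.5–9.7% at m = 5 and stays at 7.3–9.5% at m = 50.

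**The case against.** **The main test may use no imputation.** The argument for MMRM and GLMM is that they handle incomplete data under MAR, in contrast to listwise deletion or LOCF. That makes sense only if they are fitted to the observed data, and then neither m nor a seed matters. This stands. But the Missing Data text sends the imputed sets to the multivariable analysis as well as the univariate one, so the protocol is ambiguous. On the multivariable side the point holds only if that text is followed.

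**The 30% is conditional.** This also stands. A reader might infer that nearly a third of this trial's conclusions hang on the seed. The planning values do not support that: over all datasets the figure is about 7% at the planned effect.

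**Five imputations are imprecise, not invalid.** Correct under Rubin's rules. A reader might infer bias or an inflated type I error, but step 4 shows neither. The inflation in step 5 comes from averaging the datasets and would persist at any m.

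**A seed is a detail for the analysis plan, and this is a feasibility study.** A seed can be left to a later document. The number five is stated here, however, and section 3.2 also sets out to assess effectiveness, judged at 0.05. Context lowers the priority without removing the point.

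**Conclusion.** The point holds as a minor one. Where imputed data feed a test, five imputations at 20% dropout leave a seed-to-seed SD of about 0.2 in the t statistic. Under Rubin's rules this changes the decision for about 30% of seeds when p is 0.03 to 0.08, and for about 7% over all datasets at effect 0.42. With 50 imputations these fall to about 13% and 2%. What is lost is reproducibility near the threshold.

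The sizes rest on a two-sided test, equal dropout by arm, correlations of 0.2 to 0.7, and a between-arm change score or ANCOVA standing in for the planned tests. The paired tests within arms and the logistic model for EQ-5D were not simulated. It would go too far to say that the figures hold whatever the pooling method, or that they apply to a mixed model on observed data.

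**What to change.** In section 3.2.7.2, Missing Data:

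1. Replace five with at least 50 imputed datasets, and record and report the seed.
2. Replace the aggregation step: analyse each dataset separately and combine the results by Rubin's rules. Raising the number alone would only stabilise an anti-conservative answer if aggregation means averaging.
3. Reconcile this text with Inferential Analyses by stating whether MMRM and logistic GLMM are fitted to the observed or the imputed data. If observed, limit the imputation to the analyses that need it.

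The cost is a few sentences and seconds of computing. No new data are needed. Some seed dependence remains at 50 (about 13% of seeds for borderline results), so a reported Monte Carlo error for the primary tests would be a useful addition.

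### The missing-data rule pools the five imputed datasets instead of their estimates, which drops between-imputation variance and conflicts with the protocol's own case for MMRM/GLMM on incomplete data

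*Protocol*

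**What the plan says.** Protocol section 3.2.7.2, part b (Missing Data), plans multiple imputation in SPSS 23 under a missing-at-random assumption: "Five imputed datasets will be generated for the monotone missing pattern". The next sentence reads: "The aggregation function in SPSS version 23 will be used to pool the five imputed datasets for univariate analysis and multivariable analysis". The section does not describe the imputation model or say whether arm is in it. It mentions no analysis of the separate datasets and no combined standard error.

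The following section, Inferential Analyses, argues differently. It criticises repeated measures ANOVA and ANCOVA for relying on listwise deletion or last observation carried forward. It then says that, "given the missingness for dropout 20%) and small sample size", "MMRM or logistic GLMM is superior in conserving the power of the current dataset", and it cites their unbiasedness under MCAR or MAR. MMRM is fixed for the outcomes, with logistic GLMM for EQ-5D. Paired tests of T0 against T1 form the univariate analysis.

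The opening of 3.2.7.2 places the statistical analysis in STATA 17 and sets the error rate: "All the data interpretation will be based on the significant level of 0.05 with a power of 80" per cent.

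**The concern.** Multiple imputation gives honest standard errors only if each completed dataset is analysed separately and the results are combined with both within- and between-imputation variance. If the five datasets are merged first, most of the imputation noise averages out. Each dropout then counts as an observed person with an unusually precise T1 value, so model standard errors are too small.

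There is also an internal conflict. The argument for a likelihood-based model under MAR has force only if the model sees incomplete data. The Missing Data section, however, sends the aggregated data to the multivariable analysis, where nothing is missing. Two analysts could each follow this protocol faithfully and report different p-values for PHQ-9, GAD-7 and EQ-5D.

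**Working it through.** **Inputs from the protocol.** 50 per arm (3.2.5: "the estimated sample size was 50 cases in each arm (after inflated with a 20 % reserved rate"), 20% missing at T1 (Inferential Analyses), m = 5 imputations (Missing Data), significance level 0.05 (3.2.7.2).

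**Assumptions, because the protocol is silent.** Two-sided test; complete T0; combining means averaging; arm and T0 in the imputation model; pre-post correlation r = 0.3 to 0.7. Each arm then has 40 observed and 10 imputed T1 values.

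**Stated figure.** The plan claims 5%. The question is whether the averaged dataset delivers it.

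**Step 1: ANCOVA, approximate, in units of the residual variance.** An averaged imputed value keeps only 1/5 of the residual variance.
- Variance the model reports: 2 × (0.8 + 0.2/5)/50 = 2 × 0.84/50 = 0.0336.
- Between-imputation variance: B = 2 × (0.2²/40 + 0.2²/10) = 2 × (0.001 + 0.004) = 0.010.
- True variance of the estimate: 2/40 + B/5 = 0.050 + 0.002 = 0.052.
- Reported SE over true SE: √(0.0336/0.052) = 0.80.
- Rejection under no effect: 2Φ(−1.96 × 0.804) ≈ 11.5%.

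**Step 2: Rubin's rules on the same imputations.** Total variance = within + (1 + 1/5)B = 2/50 + 1.2 × 0.010 = 0.040 + 0.012 = 0.052, which equals the true variance.

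**Step 3: difference in change scores.** On completed data this equals the two-time-point MMRM interaction. Take unit SD and r = 0.5.
- Change variance is 2(1 − r) = 1.0 if observed, and (1 − r)² + (1 − r²)/5 = 0.25 + 0.15 = 0.40 if averaged.
- Reported variance: 2 × (0.8 × 1.0 + 0.2 × 0.40)/50 = 0.0352.
- True variance: 2 × (0.75/40 + 0.25/50) + 0.010 × 0.75/5 = 0.0475 + 0.0015 = 0.0490.
- SE ratio: √(0.0352/0.0490) = 0.85. Rejection: 2Φ(−1.96 × 0.848) ≈ 9.7%.

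**Step 4: simulation with no true effect** (10,000 trials per cell, 50 per arm, 20% missing, m = 5, averaged dataset, arm in the imputation model):

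| r | Change score: rejection (SE ratio) | ANCOVA: rejection (SE ratio) |
|---|---|---|
| 0.3 | 8.8% (0.87) | 11.8% (0.80) |
| 0.5 | 9.8% (0.84) | 11.9% (0.79) |
| 0.7 | 10.2% (0.83) | 11.6% (0.80) |

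Across all runs, including smaller ones and baseline-dependent dropout, the ranges are 8-12% for the change score and 11-13% for ANCOVA. The paired test within the intervention arm rejects 8.5-12%. Rubin's rules give 4.4-5.5%. Analysing only the observed T1 data gives 4.5-5.5%.

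**Step 5: sensitivity.**
- Missingness: about 6.5-8.5% rejection at 10% missing and 12-17.5% at 30% missing.
- Arm left out of the imputation model, 20% missing: the between-group test rejects about 4-6% and the within-arm paired test about 7-8%. Dropouts in both arms are then imputed from one common regression, so the estimated effect is about 0.8 × true + 0.2 × 0. An illustrative effect of 0.42 would become 0.8 × 0.42 = 0.336.

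**The case against.** The best defence has three parts.

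First, the protocol never says that values are averaged, and it does say the steps of multiple imputation will be followed. Aggregation may be loose wording for combining results. That is possible, but the sentence names the datasets as the thing pooled, and no combination of estimates appears anywhere. The wording needs correcting under either reading.

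Second, the case made for MMRM/GLMM makes sense only for incomplete data, so the models may be meant to run on the unimputed data. The inflation would then not reach them. A reader might infer that every primary and secondary p-value is anti-conservative, but the documents do not support that, because they do not settle which dataset the models receive. What stands is that one section assigns the aggregated data to the multivariable analysis while the next argues from incomplete data.

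Third, the inflation depends on arm being in the imputation model, which is not stated. A reader might infer a flat error rate of 10-13%. Without arm the between-group rate stays near 5%, and the top of that range belongs to ANCOVA, which the protocol considers but does not choose. This objection stands against a flat figure. It does not rescue the rule, because omitting arm biases the effect towards zero and still leaves the paired tests inflated.

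A reader might also infer that an averaged EQ-5D status would be a fraction, unusable in a logistic model. The protocol dichotomises a continuous index at 0.928. Averaging the index and then applying the cut-off still gives 0 or 1, so that argument fails.

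**Conclusion.** The rule as written is wrong and should be corrected before analysis. Pooling datasets discards between-imputation variance, and the Missing Data and Inferential Analyses sections cannot both govern the same models.

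The defect is certain on the literal wording; its size is conditional. With 20% missing, aggregated data feeding the models, arm in the imputation model and correlations of 0.3 to 0.7, a nominal 5% test runs at roughly 8-12% for the planned two-time-point comparison. It runs at 11-13% if ANCOVA is used, and the within-arm paired tests are inflated too. If arm is omitted, the harm between groups is attenuation by about the missing fraction rather than false positives. If MMRM/GLMM is fitted to unimputed data, those models are unaffected and the problem is confined to whatever is run on the aggregated data, such as the paired tests.

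**What to change.** Delete the aggregation sentence. State that MMRM and logistic GLMM are fitted to the observed, unimputed data, as Inferential Analyses already argues. Wherever imputation is kept (paired tests, a sensitivity analysis), state that the imputation model includes arm and T0 scores, that each imputed dataset is analysed separately, and that estimates and standard errors are combined by Rubin's rules. Changing the software or raising the number of imputations is optional: five imputations with Rubin's rules already restore about 5%.

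Cost: a couple of sentences in 3.2.7.2 and a few lines of code. Intervals from imputed data become somewhat wider, as they should. No change to design, sample or data collection is needed.
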